2.1.3.2.1 HRQOL Instruments: Haem-A-QOL and Haemo-QOL

The Haemophilia Quality of Life Questionnaire for Adults (Haem-A-QOL) and Haemophilia Quality of Life Questionnaire for Children and Adolescents (Haemo-QOL) are psychometrically tested QOL assessment instruments for patients with hemophilia. The Haem-A-QOL are provided to patients ≥ 17 years of age, and includes 46 items contributing to 10 QOL domains (physical health, feelings, view of yourself, sports and leisure, work and school, dealing with hemophilia, treatment, future, family planning, partnership and sexuality). Scoring for each item is based on a 5-point Likert scale (never, rarely, sometimes, often, and all the time), and higher scores represent greater impairment.

The Haemo-QOL (Children's short version for age groups II/III [8-16 years of age]) are provided to patients < 17 years of age.

Both Haem-A-QOL and Haemo-QOL test are assessed at Month -6, Day 1 and Month 7 visit.

2.1.4 Safety endpoints

The safety analysis will be based on the reported adverse events (AEs) including SAEs and other safety information, such as clinical laboratory data, vital signs, weight and height, physical examination, ECG findings, and ADA detection/assessment.

Observation period:

- Factor/BPA prophylaxis period is defined as the time from enrollment (Month-6 visit) up to the 1st dose of fitusiran.
- Fitusiran prophylaxis period is defined as the time after the 1st dose of fitusiran up to the end of the study (defined as last protocol planned visit). It includes the following 2 periods:
 - Fitusiran treatment period is defined as the time after the 1st dose of fitusiran to the EOS/ET visit,
 - Follow up period is defined as the time after Fitusiran treatment period up to the end of the study.

The treatment-emergent adverse event period equals fitusiran prophylaxis period.

On-study observation period includes both factor/BPA prophylaxis period and fitusiran prophylaxis period.

2.1.4.1 Adverse events variables

AE observation period:

- Pretreatment AEs are defined as those AEs that developed or worsened during factor/BPA prophylaxis period.
- Treatment emergent AEs are defined as those AEs that developed or worsened during treatment-emergent adverse event period.

All adverse events (including serious adverse events [SAEs] and adverse events of special interests [AESI]) will be coded to a lower-level term (LLT), preferred term (PT), high-level term (HLT), high-level group term (HLGT), and associated primary system organ class (SOC) using the version of Medical Dictionary for Regulatory Activities (MedDRA) in effect at the time of database lock.

Record the occurrence of adverse events (including serious adverse events and adverse events of special interest) from the time of signed informed consent until the end of the study.

Adverse events of special interest include the following terms:

- ALT or AST elevations $>3 \times$ ULN,
- Suspected or confirmed thrombosis,
- Severe or serious ISRs, ISRs that are associated with a recall phenomenon (reaction at the site of a prior injection with subsequent injections), or those that lead to temporary dose interruption or permanent discontinuation of fitusiran,
- Systemic IARs (injection associated reactions), defined as hypersensitivity reactions which are related or possibly related to IMP.
- Cholecystitis
- Cholelithiasis

The cholecystitis and cholelithiasis will be identified by medical adjudication on a listing of adverse event searched with SMQ Biliary disorders (broad) and SMQ Acute pancreatitis (narrow), since these two AESIs were added in protocol V6.0 near the end of study.

2.1.4.2 Deaths

The deaths observation periods are per the observation periods defined above.

- Death on-study: deaths occurring during the on-study period,
- Death on factor/BPA prophylaxis: deaths occurring during the factor/BPA prophylaxis period,
- Death on fitusiran treatment: deaths occurring during the fitusiran treatment period,
- Death on follow up: death occurring during the follow up period.

2.1.4.3 Laboratory safety variables

Clinical laboratory data consists of blood analysis, including hematology, clinical chemistry, and urinalysis. Clinical laboratory values after conversion are analyzed in standard international units and international units are used in listings and tables.

Blood samples for clinical laboratories are taken at screening visit, every month in factor/BPA prophylaxis period, every half month in the first two months of fitusiran treatment period and then every month in the remaining study period.

The laboratory parameters are classified as follows:

- Hematology
 - Red blood cells and platelets: hemoglobin, hematocrit, mean corpuscular volume, mean corpuscular hemoglobin concentration, mean corpuscular hemoglobin, red blood cell count, platelet count
 - White blood cells: white blood cell (WBC) count, neutrophils, lymphocytes, monocytes, basophils, eosinophils, CD4 in HIV-positive patients (at screening only)
 - Coagulation: Prothrombin time, Activated partial thromboplastin time, INR, Fibrinogen, D-dimer, Prothrombin fragment 1, 2
- Clinical chemistry
 - Metabolism: glucose, albumin
 - Electrolytes: sodium, potassium, chloride, calcium, phosphate, Carbon dioxide
 - Renal function: creatinine and eGFR (using the MDRD formula), blood urea nitrogen (BUN)
 - Liver function: aspartate aminotransferase (AST), ALT, ALP, GGT, bilirubin (total and direct)
- Factor Activity (are assessed at screening only): FVIII activity for patients with hemophilia A, FIX activity for patients with hemophilia B
- Hepatic tests (are assessed at screening and Day 1 visit):
 - Hepatitis A, including: HAV antibody IgM and IgG
 - Hepatitis B, including: HBc antibody IgM and IgG
 - Hepatitis C, including: HCV antibody and HCV RNA PCR - qualitative and quantitative assays
 - Hepatitis E, including: HEV antibody IgM and IgG
- Thrombophilia Screening (are assessed at screening only): Protein C deficiency, Protein S deficiency, Factor V Leiden (genetic testing), Prothrombin mutation (genetic testing)

Urine samples are collected as follows:

- Urinalysis (assessed at screening, Month -6 and Month 7 visit): Visual inspection for appearance and color, pH (dipstick), ketones, protein, glucose, RBCs, urobilinogen, bilirubin, Nitrite, microscopic (if clinically indicated), Leukocytes, specific gravity.

2.1.4.4 Physical examination and vital signs variables

Physical examination and vital signs are done at screening visit, every month in factor/BPA prophylaxis period, every half month in the first two months of fitusiran treatment period and then every month in the remaining study period.

Physical examination may be full or directed.

Full physical examinations include general appearance, head, eyes, ears, nose and throat; respiratory, cardiovascular, gastrointestinal, musculoskeletal, and dermatological systems; thyroid, lymph nodes, and neurological status.

Directed physical examinations include systems associated or common for signs and symptoms of thrombosis, bleeding, and arthropathy: neurologic, chest/respiratory, heart/cardiovascular, dermatological/skin, gastrointestinal/liver, and musculoskeletal/extremities. Other organ systems may be evaluated as indicated by patient symptoms. In patients undergoing a surgical procedure, a directed physical examination will also be performed as specified in the Perioperative Schedule of Assessments in the protocol.

A full physical examination is done at screening only; a directed physical exam is done at all other visits.

Physical examination notes regarding any observed abnormalities are recorded on the eCRF.

Vital signs include blood pressure, heart rate, body temperature, and respiratory rate. Vital signs are measured predose in the seated or supine position, after the patient has rested comfortably for 10 minutes.

Body temperature is recorded in degrees Celsius. Heart rate is counted for a full minute and recorded in beats per minute, and respiration rate is counted for a full minute and recorded in breaths per minute.

For the safety of the patient, additional vital sign assessments may be added at the discretion of the Investigator.

Vital signs results are recorded in the eCRF.

Measurements of weight and height are also collected at above scheduled visits for physical examination and vital signs.

2.1.4.5 Electrocardiogram variables

Triplicate standard 12-lead ECGs, with readings approximately 1 minute apart, are recorded at screening, Month -6, Day 1, Month 5 and Month 7 visits.

The electrophysiological parameters assessed are rhythm, ventricular rate, RR interval, PR interval, QRS duration, QT interval, Bazett-corrected QT interval (QTcB), and Fridericia corrected QT interval (QTcF).

The Investigator or qualified designees review all ECGs to assess whether the results have changed since the Day 1 visit and to determine the clinical significance of the results. These assessments are recorded on the eCRF. Additional ECGs may be collected at the discretion of the Investigator. Recordings are archived according to the Study Manual.

2.1.5 Pharmacokinetic variables

For all patients

- Plasma PK parameters are estimated using a population PK approach. The population PK analysis is described in a separate population PK analysis plan

For patients from East Asian sites only

- In addition to population PK analysis, plasma PK parameters for the patients from the East Asian sites only are also estimated using non-compartmental analysis. The plasma PK parameters include, but may not be limited to:
 - Maximum plasma concentration (C_{max})
 - Time to maximum plasma concentration (t_{max})
 - Elimination half-life ($t_{1/2\beta}$)
 - Area under the concentration-time curve (AUC)
 - Apparent clearance (CL/F)
 - Apparent volume of distribution (V/F)
- Fitusiran levels in 0-24 h urine are reported as cumulative amount of drug excreted unchanged in urine (A_e)
- Additional PK parameters for plasma and/or urine may also be calculated, if considered appropriate

2.1.6 Pharmacodynamic endpoints

In this study AT activity level and thrombin generation (TG) over time are collected as measurements of PD effect and coagulation assessments are collected for exploratory analyses of PD effect.

AT activity level and TG are assessed at screening, Day 1 and then every half month in the first two months of fitusiran treatment period and then every month in the remaining study period.

During the factor/BPA prophylaxis period (before fitusiran treatment), patients undergo a coagulation and peak thrombin/thrombin generation response assessment with timed blood collections both before and following a dose of their routine factor/BPA prophylaxis doses.

2.1.7 Exploratory endpoints

Exploratory endpoints include:

- Change in the following in the fitusiran treatment period:
 - Treatment Satisfaction Questionnaire for Medication (TSQM) domain scores
 - Haemophilia Activities List (HAL) score

- Paediatric HAL (pedHAL) score
- EuroQol -5 Dimensions (EQ-5D) score
- Haemo-QOL score
- Hemophilia Joint Health Score (HJHS)
- Number of target joint bleeding episodes
- Incidence and titer of antidrug antibodies to fitusiran in the fitusiran treatment period
- AT activity level over time
- TG over time
- Fitusiran plasma levels
- Change in patient resource use (eg, work/school attendance, visits to doctor/hospital)

2.2 DISPOSITION OF PATIENTS

This section describes patient disposition for both patient study status and the patient analysis populations.

Screened patients are defined as any patient who signed the informed consent.

Enrolled patients are defined as any patient with a signed informed consent form (ICF) who met all the inclusion criteria and none of the exclusion criteria.

This is an open-label, single-arm, before and after switch study without randomization.

For patient study status, the total number of patients in each of the following categories is presented in the clinical study report using a flowchart diagram or summary table:

- Screened patients
- Screened failure patients and reasons for screen failure (if data are available)
- Enrolled patients
- Patients treated without entering factor/BPA prophylaxis period
- Patients who entered factor/BPA prophylaxis period (run-in)
- Patients who completed the factor/BPA prophylaxis period
- Patients who did not complete factor/BPA prophylaxis period, with corresponding reasons
- Patients who did not complete factor/BPA prophylaxis period, with corresponding reasons due to Covid-19
- Patients treated after factor/BPA prophylaxis period
- Patients who completed the study treatment (7-month treatment period)

- Patients who discontinued study treatment by main reason for permanent treatment discontinuation
- Patients who discontinued study treatment by main reason for permanent treatment discontinuation due to Covid-19
- Patients who completed the study
- Patients who did not complete the study but complete the 7-month treatment period
- Patients who did not complete the study, with corresponding reasons.
- Patients who did not complete the study, with corresponding reasons due to Covid-19.

For all categories of patients (except for the screened categories), percentages are calculated using the number of enrolled patients as the denominator. Reasons for treatment discontinuation are supplied in tables giving numbers and percentages.

All critical or major deviations potentially impacting efficacy analyses, and other major or critical deviations are summarized in tables giving numbers and percentages.

Additionally, the analysis populations (analysis sets) for safety and efficacy are summarized in a table.

- Efficacy Analysis Set 1
- Efficacy Analysis Set 2
- Per-protocol Analysis Set
- Safety Analysis Set 1
- Safety Analysis Set 2
- Operative Procedure Analysis Set
- Covid-19 Unaffected Set

2.3 ANALYSIS POPULATIONS

The populations (analysis sets) are defined as follows:

- **Safety Analysis Set 1 (SAS 1)** : All patients who enrolled and then received any dose of fitusiran before dose resumption. Safety Analyses for patients who were treated with fitusiran in 80mg QM dose regimen before dose resumption will be conducted using the Safety Analysis Set 1 unless otherwise specified.
- **Safety Analysis Set 2 (SAS 2)** : All patients who enrolled and then received any dose of Fitusiran after dose resumption. Safety Analyses for patients who were treated with fitusiran in 50mg Q2M after dose resumption will be conducted using the Safety Analysis Set 2 unless otherwise specified.

- **Efficacy Analysis Set 1 (EAS1) 1:** All patients in the safety analysis set 1 who received factor or BPA prophylaxis and any dose of fitusiran before dose resumption. Efficacy Analyses before dose resumption will be conducted using EAS 1 unless otherwise specified.
- **Efficacy Analysis Set 2 (EAS 2) :** All patients in the safety analysis set 2 who received factor or BPA prophylaxis and any dose of fitusiran. Efficacy Analyses after dose resumption will be conducted using EAS 2 unless otherwise specified.
- **Per-protocol Analysis Set (PPS):** All patients in the EAS 1 who do not have protocol deviations in the following categories:
 - Failure to meet key Eligibility criteria, which will be identified prior to database lock,
 - Other protocol deviations that might significantly affect the completeness, accuracy, and/or reliability of the bleeding data.

The major or critical deviations to be considered are as follows.

- The participant is not male and/or is younger than 12 years, but the participant was enrolled.
- The participant does not have severe hemophilia A or B as evidenced by a laboratory FVIII level $<1\%$ or FIX level $\leq 2\%$ at Screening or by documented medical record, but the participant was enrolled.
- The participant does not have a minimum of:
 - 2 bleeding episodes requiring bypassing agent treatment within the last 6 months prior to Screening for participants with inhibitory antibodies to FVIII or FIX (Cohort A),
 - 1 bleeding episode requiring factor treatment within the last 12 months prior to Screening for patients without inhibitory antibodies to FVIII or FIX (Cohort B), but the participant was enrolled.
- The participant was enrolled, but does not meet either the definition of inhibitor or non-inhibitor as below:

Inhibitor, as evidenced by:

- Use of bypassing agents for prophylaxis and for any bleeding episodes for at least the last 6 months prior to Screening,
- Meeting one of the following Nijmegen-modified Bethesda assay results criteria:
 - Inhibitor titer of ≥ 0.6 BU/mL at Screening, or
 - Inhibitor titer of <0.6 BU/mL at Screening with medical record evidence of 2 consecutive titers ≥ 0.6 BU/mL, or
 - Inhibitor titer of <0.6 BU/mL at Screening with medical record evidence of anamnestic response,

- The subgroup of patients in Cohort A patients must additionally meet the following criteria to be eligible to start treatment with fitusiran directly after the screening period:
 - Hemophilia B with inhibitory antibody to FIX as defined above and
 - Not responding adequately to BPA treatment (historical ABR ≥ 20) prior to enrollment and
 - In the opinion of the Investigator, with approval of sponsor medical monitor, 6-month BPA prophylaxis period should be omitted.

Non-inhibitor, as evidenced by:

- Use of factor concentrates for prophylaxis and for any bleeding episodes for at least the last 6 months prior to Screening,
- Meeting each of the following criteria:
 - Nijmegen-modified Bethesda assay inhibitor titer of < 0.6 BU/mL at Screening and
 - No use of bypassing agents to treat bleeding episodes for at least the last 6 months prior to Screening and
 - No history of immune tolerance induction therapy (ITI) within the past 3 years prior to Screening,
- The participant did not receive prescribed prophylactic treatment of hemophilia with factor concentrates or bypassing agents for at least 6 months prior to Screening, or did not receive a prophylactic regimen consistent with the approved prescribing information for the product or local recommendations, allowing for adjustment to individual patient response, and designed to decrease spontaneous bleeding, but the participant was enrolled.
- The participant has known co-existing bleeding disorders other than hemophilia A or B, but the participant was enrolled
- The participant discontinued prophylactic treatment or withdrew consent during the factor/bypassing agent prophylaxis period, but participant was not withdrawn from the study.
- The participant continued or reinitiated use of factor concentrates or bypassing agents as prophylaxis for bleeding episode prevention, during the fitusiran prophylaxis treatment period but the study drug was not discontinued.
- The participant did not administer prophylaxis therapy with minimum frequency as per protocol (table 5) during the prophylaxis period:
 - Standard half-life FVIII (Twice weekly)
 - Extended half-life FVIII (Once weekly)
 - Standard half-life FIX (Once weekly)
 - Extended half-life FIX (Once biweekly)

- aPPC (Twice weekly)
- rFVIIa (Every other day)
- **Operative Procedure Analysis Set:** All SAS 1 patients underwent at least 1 operative procedure during the study.
- **Covid-19 Unaffected Set:** All EAS 1 patients who had no major or critical protocol deviations due to Covid-19 at any visits up to end of study (Month 7).

In addition:

Patients treated without entering factor/BPA prophylaxis period are included in the safety analysis set, but are not part of the efficacy analysis set; however, their efficacy data are presented separately.

Patients who entered factor/BPA prophylaxis period but not treated with fitusiran are not included in either safety analysis set or efficacy analysis set, however, their safety data are reported separately.

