5.3 REMOVAL FROM THERAPY OR ASSESSMENT

Patients or their legal guardian (in case patient is a minor) are free to discontinue treatment or withdraw from the study at any time and for any reason, without penalty to their continuing medical care. Any discontinuation of treatment or withdrawal from the study must be fully documented in the electronic case report form (eCRF) and should be followed up by the Investigator. The Investigator may withdraw a patient at any time if this is considered to be in the patient's best interest.

Patients who discontinue their prophylactic treatment or withdraw consent during the factor or BPA prophylaxis period (BPA prophylaxis period is not applicable for the subgroup of Cohort A patients who are not responding adequately to BPA prophylaxis treatment) will be withdrawn from the study. For the United States specific requirements, see [Section 11.6.1.2](#).

Procedures for discontinuation of study drug and/or withdrawal from the study during the fitusiran treatment period are described in [Section 5.3.1](#) and [Section 5.3.2](#), respectively.

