8.2.1 Populations to be analyzed

The populations (analysis sets) are defined as follows:

- **Safety Analysis Set:** All patients who enrolled and then received any dose of fitusiran.
- **Efficacy Analysis Set (EAS):** All patients in the safety analysis set who received both factor or BPA prophylaxis and any dose of fitusiran (Addressed in more detail in SAP).
- **Per-protocol Analysis Set (PPS):** All patients in the EAS who had no major protocol deviations. Major deviations will be specified in the SAP.
- **PK Analysis Set:** All patients who received any dose of study fitusiran and have at least 1 postdose blood sample for PK parameters and have evaluable PK data.
- **COVID-19 Unaffected Set:** All patients who had no major or critical protocol deviations due to COVID-19 at any visit up to the end of study (Month 7).
- The subgroup of Cohort A patients who are not responding adequately to BPA prophylaxis treatment will be included in the safety analysis set but will not be part of the efficacy analysis set; however, their efficacy data will be presented separately.

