2.4.5.1 Analyses of adverse events

Generalities

The focus of adverse event reporting is on treatment-emergent adverse events and pre-treatment adverse events. Adverse events occurring in the screening period are analyzed separately.

If an adverse event date/time of onset (occurrence, worsening, or becoming serious) is incomplete (missing time, day, month or year), an imputation algorithm is used to classify the adverse event as pretreatment and treatment-emergent. The algorithm for imputing date/time of onset is conservative and classifies an adverse event as treatment emergent unless there is definitive information to determine it is pretreatment or posttreatment. Details on classification of adverse events with missing or partial onset dates are provided in [Section 2.5.3](#).

AEs are summarized by observation period (factor/BPA prophylaxis period and fitusiran prophylaxis period) and by the numbers and percentages of patients reporting at least one AE, having at least one AE by primary System Organ Class (SOC) and Preferred Term (PT). A patient with multiple occurrences of an AE is counted only once in the respective AE category. Patients who report multiple occurrences of the same AE (preferred term) are classified according to the most related or most severe occurrence, respectively.

All AE summaries are presented (frequency counts and percentages) by system organ class and/or preferred term, unless specified otherwise. The SOC is presented by internationally agreed order and the preferred term is sorted within each SOC in decreasing order of frequency in fitusiran prophylaxis period.

Analysis of all adverse events

An overall summary of AEs includes the number and percentage of patients with any:

- AE
- AE assessed by the Investigator as related to study drug (fitusiran only, possibly related or definitely related)
- severe AE
- severe AE related to study drug
- serious AE (SAE)
- SAE related to study drug
- AE/SAE of special interest
- Study drug related AE/SAE of special interest
- AE/SAE leading to study drug discontinuation
- Study drug related AE/SAE leading to study drug discontinuation
- AE/SAE leading to study withdrawal

- Study drug related AE/SAE leading to study withdrawal
- SAE with a fatal outcome.
- AEs potentially consistent with COVID-19

The overall summary of AEs will also be provided by hemophilia type.

Tabulations by SOC and PT are produced for the following:

- AEs
- AEs by severity
- AEs by hemophilia type
- SAEs

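### The factor/BPA column of the by-period harm tables uses a safety set that requires a fitusiran dose, so control-period deaths are zero and AE withdrawals nearly zero by construction

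*SAP*

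**What the plan says.** **Who is in the set.** SAP 2.3 defines Safety Analysis Set 1 (SAS 1) as "All patients who enrolled and then received any dose of fitusiran before dose resumption". SAS 2 applies the same condition after dose resumption. Protocol 8.2.1 has the same rule: "All patients who enrolled and then received any dose of fitusiran". SAP 2.3 then says that "Patients who entered factor/BPA prophylaxis period but not treated with fitusiran are not included in either safety analysis set or efficacy analysis set", and adds: "however, their safety data are reported separately". For the Cohort A subgroup that skips the control period, it says: "Patients treated without entering factor/BPA prophylaxis period are included in the safety analysis set".

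**What is tabulated on it.** SAP 2.4.5 assigns all safety analyses to SAS 1 or SAS 2 unless otherwise specified, and gives never-dosed patients a separate listing. SAP Appendix A names SAS 1 for adverse events. SAP 2.4.5.1 says: "AEs are summarized by observation period (factor/BPA prophylaxis period and fitusiran prophylaxis period"). Its overview includes SAEs, fatal SAEs, and AEs or SAEs leading to study withdrawal. In the SOC/PT tabulations, drug-related and drug-discontinuation tables are limited to the fitusiran period; the study-withdrawal tables are not. SAP 2.1.4.2 also defines a control-period death category: "Death on factor/BPA prophylaxis: deaths occurring during the factor/BPA prophylaxis period".

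**When the control period ends.** SAP 2.1.4 closes the factor/BPA observation period at the first fitusiran dose. Protocol 5.3 addresses early leavers: "Patients who discontinue their prophylactic treatment or withdraw consent during the factor or BPA prophylaxis period" are withdrawn from the study.

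**The concern.** Membership of the set is decided by something that happens after the control period. A patient who dies on factor or BPA prophylaxis, or stops it because of an adverse event, never reaches a fitusiran dose and so drops out of the table that describes that period. The same event on fitusiran is counted.

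The rows affected are the most serious ones: death, and adverse events that end participation. A reader of the adjacent columns would see zeros under factor/BPA and could take them for an observed result, when the definition allows nothing else.

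**Working it through.** The plan states no figure for this point, so there is none to reproduce. The check is the set logic, followed by the size of one displaced event.

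**1. Set logic**

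- SAS 1 and SAS 2 require a fitusiran dose (SAP 2.3).
- The factor/BPA period ends at the first dose (SAP 2.1.4).
- Someone who dies or leaves the study during that period is never dosed, so is in neither set.

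| Row, factor/BPA column | Possible value on SAS 1 |
|---|---|
| Death during the period | exactly 0 |
| Study withdrawal during the period | exactly 0 |
| AE leading to study withdrawal | near 0: only an AE that began in the control period and led to withdrawal after dosing |
| SAE with fatal outcome | near 0: only an SAE that began in the control period and was fatal after dosing |
| Other AEs and SAEs | those of patients later dosed only |

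For the first four rows the direction is fixed: they cannot be too high. For the last row, never-dosed patients leave both numerator and denominator, so it is understated only if those who left had more events than those who stayed. That is plausible but not shown.

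**2. Size of one displaced event**

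Inputs: about 30 patients in Cohort A, about 50 in Cohort B and about 80 in total, with no more than 4 direct-entry patients, all in Cohort A (SAP 1.1, Protocol 4.3). With 4 direct entries, those entering the factor/BPA period number 30 − 4 = 26 in Cohort A, 50 in Cohort B and 80 − 4 = 76 pooled.

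- Cohort A: 1/26 = 3.8%
- Cohort B: 1/50 = 2.0%
- Pooled: 1/76 = 1.3%

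For a control-period death, the planned table prints 0 in each case.

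**3. Chance that at least one such event occurs**

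The documents give no risk, so p is an assumption. Among 76 entrants the chance is 1 − (1 − p)^76:

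- p = 1%: 53%
- p = 2%: 79%
- p = 5%: 98%

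**4. Direct-entry dilution (conditional)**

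SAP 2.4.5 ties the denominators for potentially clinically significant abnormalities to patients assessed in each period. SAP 2.4.5.1 states no such rule for AE percentages. If the full set of N is used and k patients have no control period, the control incidence is multiplied by (N − k)/N.

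| k | Cohort A, N = 30 | Pooled, N = 80 |
|---|---|---|
| 0 | 1.000 | 1.000 |
| 2 | 0.933 | 0.975 |
| 4 | 0.867 | 0.950 |

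At k = 4, a control incidence of 30% prints as 0.30 × 26/30 = 26.0% in Cohort A and 0.30 × 76/80 = 28.5% pooled. This also lowers the control column, the same direction as the survivor effect.

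**The case against.** **The events remain visible.** This is correct. SAP 2.3 and 2.4.5 report or list never-dosed patients separately. SAP 2.4.5.1 plans by-patient listings of deaths, SAEs, and AEs leading to drug discontinuation or study withdrawal. SAP 2.2 counts patients who did not complete the factor/BPA period, with reasons, as a percentage of enrolled patients. A reader might infer that control-period deaths disappear from the report; the documents do not support that. What stands is narrower: none of these outputs changes the percentages in the by-period tables.

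**No safety contrast is planned.** The bleeding, quality-of-life and consumption objectives are worded relative to prophylaxis. The safety objective is only to characterize fitusiran (Protocol 2.2, SAP 1.2.2), and SAP 2.4.5 calls the safety analysis essentially descriptive. It would therefore be too strong to say that a planned comparison is invalid, or that nothing about relative safety can be learned. The fitusiran column, which serves the objective, is untouched. The by-period layout still invites the comparison.

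**Displacement may be rare.** Entrants had to be prescribed and adherent to prophylaxis for at least 6 months before Screening (Protocol 5.1, I 05 and I 06), so new intolerance may be uncommon. The documents do not show that even one event is displaced.

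**The dilution is not established.** Also correct. Membership of SAS 1 does not show that direct-entry patients would be counted in a factor/BPA percentage; the SAP is silent on this.

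**A new set would not make the columns comparable.** This stands too. The fitusiran prophylaxis period runs to the end of the study and includes AT follow-up (SAP 2.1.4). That is 7 months of treatment plus up to 6 more for patients not entering the extension (Protocol 4.2), against 6 months of control.

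**Conclusion.** The concern holds for the by-period tables. On SAS 1 the factor/BPA column cannot contain a control-period death and can contain almost no AE withdrawal, while the fitusiran column can contain both. Any such event therefore tilts the tables against fitusiran. Each one is worth 3.8%, 2.0% or 1.3% of the control column (Cohort A with 4 direct entries, Cohort B, pooled) at planned sizes. If nobody died or left because of an adverse event before dosing, those rows are not distorted. The actual number is not in the documents.

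The direct-entry dilution is secondary and rests on an unstated denominator: at most 13.3% relative in Cohort A and 5.0% pooled, and nil with no direct-entry patients.

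The finding does not mean that the safety data are missing, that the fitusiran safety profile is misreported, or that the raw percentages would become directly comparable once the set is changed.

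**What to change.** In SAP 2.3 and 2.4.5:

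1. Define a prophylaxis-period safety set: all patients who entered the factor/BPA period, later dosed or not, excluding direct-entry patients.
2. Use it as numerator and denominator for the factor/BPA column of the AE, SAE, death and study-withdrawal tables. This also settles the AE denominator for that column.
3. Keep SAS 1 for the fitusiran column.
4. Add a supplementary paired table in patients who have both periods.
5. Note under the tables that the observation periods differ in length, because the fitusiran prophylaxis period includes AT follow-up, so raw percentages are still not directly comparable.

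The cost is SAP wording, one population flag and the supplementary table. No new data are needed, since AEs are recorded from consent (SAP 2.1.4.1). The downside is that the two columns no longer hold identical patients, which the paired table covers.
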